10.2 Baseline Values

Unless otherwise noted, baseline is defined as the last nonmissing value recorded prior to the first application of study drug. If time is not recorded and the assessment was on the same day as the first application of study drug, then it will be assumed the assessment occurred prior to the application of study drug.

10.3 Adjustments for Covariates

The model for the primary efficacy will include adjustments for the following covariates: investigator type (dermatologist vs other), household number of randomized subjects (1 subject per household vs 2 subjects per household), age, and baseline lesion count.

10.4 Handling of Dropouts or Missing Data

In analyses based on response, a missing response will be considered a nonresponder.

For a sensitivity analysis, subjects with missing lesion count at Week 12 but who demonstrated complete clearance at the last collected lesion assessment will be counted as responders.

10.5 Interim Analysis and Data Monitoring

When approximately 200 subjects (cumulative across studies NI-MC301 and NI-MC302) have completed 4 weeks of treatment, a DSMB will review all available unblinded safety data (including patch testing). All responsibilities of the DSMB and details of the analysis and data to be reviewed is detailed in the DSMB charter.

10.6 Examination of Subgroups

Subgroup analyses of complete clearance at Week 12 for investigator type (dermatologist vs other) and household number of randomized subjects (1 subject per household vs 2 subjects per household), and will be presented in a forest plot for the ITT Population. An additional subgroup analysis of complete clearance at Week 12 for age (≤ 1 year old, > 1 to ≤ 2 years old, > 2 to ≤ 6 years old, > 6 to ≤ 12 years old, > 12 to ≤ 18 years old, > 18 years old) and MC disease duration prior to baseline (≤ 6 months vs > 6 months) will be summarized descriptively for the ITT Population.

10.7 Multiple Comparison/Multiplicity

The familywise error rate with respect to the primary endpoint and secondary endpoint will be strongly controlled at the alpha=0.05 level using a fixed-sequence method testing strategy. If the primary endpoint is not statistically significant at the alpha=0.05 level, the secondary efficacy

endpoint will be considered not significant. If the primary endpoint is statistically significant at the alpha=0.05 level, then the secondary efficacy endpoint will be analyzed. If the secondary efficacy endpoint fails to reach statistical significance at the alpha=0.05 level, it will be considered not statistically significant.

10.8 Multicenter Studies

This is a multicenter study, having approximately 35 centers participating in the study. The center effects will be investigated in the primary statistical analysis model.

11. METHODS OF EFFICACY ANALYSIS

11.1 Primary Efficacy Analysis

The primary efficacy comparison will test the following hypotheses:

H_0 : The proportion of subjects with complete clearance is equal between SB206 12% QD and Vehicle;

H_1 : The proportion of subjects with complete clearance is different between SB206 12% QD and Vehicle.

The primary efficacy model will be the following for π_{H_i} as the probability of complete clearance for the i^{th} subject in household H:

$$\pi_{H_i} = \frac{e^{(\beta_0 + \beta_1 * X_{H_{i1}} + \beta_2 * X_{H_{i2}} + \beta_3 * X_{H_{i3}} + \beta_4 * X_{H_{i4}} + \beta_5 * X_{H_{i5}})}}{1 + e^{(\beta_0 + \beta_1 * X_{H_{i1}} + \beta_2 * X_{H_{i2}} + \beta_3 * X_{H_{i3}} + \beta_4 * X_{H_{i4}} + \beta_5 * X_{H_{i5}})}}$$

where H = Household, i = subject within the household, β_0 is the intercept,

$$X_{H_{i1}} = \begin{cases} 1, & \text{if treatment is SB206} \\ 0, & \text{if treatment is Vehicle} \end{cases}$$

$$X_{H_{i2}} = \begin{cases} 1, & \text{if subject is from a 2 subject household} \\ 0, & \text{if subject is from a 1 subject household} \end{cases}$$

$$X_{H_{i3}} = \begin{cases} 1, & \text{if subject is from a Dermatology site} \\ 0, & \text{if subject is from an Other site} \end{cases}$$

$X_{H_{i4}}$ is the subject's baseline lesion count, and $X_{H_{i4}}$ is the subject's age at baseline; treatment will be included in the class statement with PARAM=REF and REF=Vehicle. The working correlation will have an exchangeable structure. The model will include a repeated statement for subject household with household ID in the class statement. Also, the data structure will be ordered according to household ID and subject ID in household.

Treatment groups will be compared using a generalized estimating equation for logistic regression with an exchangeable working correlation structure. The model will include treatment, investigator type (dermatologist vs other), household number of randomly assigned subjects (1 subject per household vs 2 subjects per household), age, and baseline lesion count as factors. The odds ratio between SB206 12% and vehicle gel, 95% confidence intervals for the odds ratio, and *P*-value for the covariate-adjusted treatment comparison will be presented; together with predicted proportions along with their associated 95% confidence interval.

As a sensitivity analysis, the above primary analysis model will be applied to the PP Population. An additional sensitivity analysis counting subjects who discontinued prior to Week 12 or have a missing lesion count assessment but who demonstrated complete clearance at the last collected lesion assessment as responders will be presented. The impact of mis-stratifications may be explored via a sensitivity analysis.

An analysis where the complete clearance response probability for any dropouts prior to Week 12 will be varied across the following scenarios (Vehicle response probability, SB206 response probability):

(0.1, 0.1)	(0.1, 0.0)			
(0.2, 0.2)	(0.2, 0.1)	(0.2, 0.0)		
(0.3, 0.3)	(0.3, 0.2)	(0.3, 0.1)	(0.3, 0.0)	
(0.4, 0.4)	(0.4, 0.3)	(0.4, 0.2)	(0.4, 0.1)	(0.4, 0.0)

An additional sensitivity analysis will be performed in a subset of the ITT population where only 1 subject from each household is chosen based on the subject with the highest number of baseline treatable MC and the oldest to break ties, if needed, to contribute to the model. A logistic regression model including treatment, investigator type, age, and baseline lesion counts will be utilized.

11.2 Secondary Efficacy Analyses

The secondary endpoint of the proportion of subjects with complete clearance of all treatable MC at Week 8 will be analyzed in the same manner as the primary endpoint. A sensitivity analysis using the PP Population will be provided.

11.3 Exploratory Analyses

The exploratory endpoints based on the proportion of subjects achieving complete clearance or 75% reduction will be analyzed in the same manner as the primary endpoint.

Since the within-household correlation is expected to be small and the change and percent change from Baseline in the number of treatable MC are exploratory, they will be analyzed using a repeated measures mixed model for the respective visits with the same covariates as the primary model together with visits and treatment by visit; an unstructured covariance matrix will be utilized. If the calculation of the percent change from baseline is influenced by outliers with

calculated values >100%, then the influence of outliers will be avoided for analysis by censoring them so that all values were in the range of -100% to 100%.

Since the within-household correlation is expected to be small and time to first complete clearance of all MC is exploratory, it will be analyzed using Kaplan-Meier methods. The number and percentage of subjects achieving complete clearance, number and percentage of censored subjects, and Kaplan-Meier estimates of first quartile, median, and third quartile will be summarized by treatment group. Differences in Kaplan-Meier curves between the treatments will be tested for significance using a stratified log-rank test.

The proportion of subjects with scarring and the proportion of subjects with keloid or hypertrophic scarring will be summarized descriptively at each visit.

The change from Baseline of the composite score from age-matched (at Baseline) DLQI/CDLQI will be summarized descriptively and separately for each questionnaire. The scoring algorithms are detailed in [Appendix A](#). Additionally, the changes from Baseline in the following subscales: Symptoms and Feelings, Daily Activities, Leisure, Work and School, Personal Relationships, and Treatment, for DLQI, and Symptoms and Feelings, Leisure, School or Holidays, Personal Relationships, Sleep, and Treatment, for CDLQI, and each question will be summarized descriptively.

The subject-reported spread of MC to household members not in the study will be summarized descriptively including a breakdown of whether or not there was any spread and then a breakdown of the amount of spread within the household at each visit at the household level.

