5. DETERMINATION OF SAMPLE SIZE

Approximately 340 subjects, 6 months of age and older, with a minimum of 3 and a maximum of 70 MC lesions at Baseline will be randomized in a 2:1 (active:vehicle) scheme. The sample size assumptions for this study were informed by the completed Phase 2 study NI-MC201 of subjects 2 years of age and older with between 3 and 70 MC lesions at Baseline. In the Intent-to-Treat (ITT) Population of the Phase 2 study, the observed rates of complete clearance at Week 12 were 18% (12/66) for vehicle and 38% (18/48) for SB206 12% QD and the covariate-adjusted treatment difference was 18%.

A sample size of 340 subjects (227 subjects in the SB206 12% QD group and 113 subjects in the vehicle group) will provide 94% power for a 2-sided alpha test of size 0.05 to detect an absolute difference of 18% when the vehicle response rate is 18%. This same sample size provides 93% power to detect a treatment difference of 18% when the vehicle response rate is 20% and 83% power when the treatment difference is 15% and the vehicle response rate is 20%.

Since the intra-cluster correlation is estimated to be small (<10%) and the average size of households is expected to be capped at roughly 1.3, the sample size is still sufficient when considering the fact that the subjects within the household may not be independent.

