5. DETERMINATION OF SAMPLE SIZE

Approximately 340 subjects, 6 months of age and older, with a minimum of 3 and a maximum of 70 MC lesions at Baseline will be randomized in a 2:1 (active:vehicle) scheme. The sample size assumptions for this study were informed by the completed Phase 2 study NI-MC201 of subjects 2 years of age and older with between 3 and 70 MC lesions at Baseline. In the Intent-to-Treat (ITT) Population of the Phase 2 study, the observed rates of complete clearance at Week 12 were 18% (12/66) for vehicle and 38% (18/48) for SB206 12% QD and the covariate-adjusted treatment difference was 18%.

A sample size of 340 subjects (227 subjects in the SB206 12% QD group and 113 subjects in the vehicle group) will provide 94% power for a 2-sided alpha test of size 0.05 to detect an absolute difference of 18% when the vehicle response rate is 18%. This same sample size provides 93% power to detect a treatment difference of 18% when the vehicle response rate is 20% and 83% power when the treatment difference is 15% and the vehicle response rate is 20%.

Since the intra-cluster correlation is estimated to be small (<10%) and the average size of households is expected to be capped at roughly 1.3, the sample size is still sufficient when considering the fact that the subjects within the household may not be independent.

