10.3 Adjustments for Covariates

The model for the primary efficacy will include adjustments for the following covariates: investigator type (dermatologist vs other), household number of randomized subjects (1 subject per household vs 2 subjects per household), age, and baseline lesion count. If there are not at least 3 responders and non-responders at each level of the stratification factors, then that stratification factor will be removed from the model. If there are fewer than 10 responders/non-responders, then neither investigator type nor household number of randomized subjects will be included in the model.

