11.3 Exploratory Analyses

The exploratory endpoints based on the proportion of subjects achieving complete clearance or 75%, 90%, or 95% reductions will be analyzed in the same manner as the primary endpoint.

Since the within-household correlation is expected to be small and the change and percent change from Baseline in the number of treatable MC are exploratory, they will be analyzed using a repeated measures mixed model for the respective visits with the same covariates as the primary model together with visits and treatment by visit; an unstructured covariance matrix will be utilized. If the calculation of the percent change from baseline is influenced by outliers with calculated values >100%, then the influence of outliers will be avoided for analysis by censoring them so that all values were in the range of -100% to 100%. If the model fails to converge, then other correlation structures will be explored.

Since the within-household correlation is expected to be small and time to first complete clearance of all MC is exploratory, it will be analyzed using Kaplan-Meier methods. The number and percentage of subjects achieving complete clearance, number and percentage of censored subjects, and Kaplan-Meier estimates of first quartile, median, and third quartile will be summarized by treatment group. Differences in Kaplan-Meier curves between the treatments will be tested for significance using a stratified log-rank test.

The proportion of subjects with scarring and the proportion of subjects with keloid or hypertrophic scarring will be summarized descriptively at each visit.

The change from Baseline of the composite score from age-matched (at Baseline) DLQI/CDLQI will be summarized descriptively and separately for each questionnaire. The scoring algorithms are detailed in [Appendix A](#). The CDLQI will be examined in the following Week 12 response categories: complete clearance, 95% reduction in lesion counts, 90% reduction in lesion counts, and subjects who did not achieve complete clearance. Additionally, the changes from Baseline in the following subscales: Symptoms and Feelings, Daily Activities, Leisure, Work and School, Personal Relationships, and Treatment, for DLQI, and Symptoms and Feelings, Leisure, School or Holidays, Personal Relationships, Sleep, and Treatment, for CDLQI, and each question will be summarized descriptively.

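### Time to clearance (SAP 11.3) is planned without a between-arm estimate or confidence interval, and five of its six Kaplan-Meier quartiles are not reached at the sponsor's own planning rates

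*Combined protocol and SAP*

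**What the plan says.** Section 11.3 has the same analysis for time to clearance in all three SAP versions in the file. It summarizes the number and percentage cleared and censored, and then "Kaplan-Meier estimates of first quartile, median, and third quartile will be summarized by treatment group". The comparison between arms is a test only: "Differences in Kaplan-Meier curves between the treatments will be tested for significance using a stratified log-rank test". The strata are not named. Appendix D adds a Kaplan-Meier plot. Section 10.1 measures time from first dose to first clearance and censors uncleared subjects at their last lesion count. Lesions are counted at Weeks 2, 4, 8 and 12 (SAP section 4).

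The primary model adjusts for investigator type, "household number of randomized subjects (1 subject per household vs 2 subjects per household), age, and baseline lesion count" (section 10.3). In section 11.3 the exploratory response endpoints follow that model, and the mixed models for change in lesion count carry the same covariates. The randomization strata are household number and investigator type only.

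The planning rates are in SAP section 5: "A sample size of 340 subjects (227 subjects in the SB206 12% QD group and 113 subjects in the vehicle group") gives "94% power for a 2-sided alpha test of size 0.05 to detect an absolute difference of 18% when the vehicle response rate is 18" percent. Further cases are 20% vs 38% (93% power) and "83% power when the treatment difference is 15% and the vehicle response rate is 20" percent. The protocol synopsis gives exploratory comparisons nominal p-values only.

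**The concern.** A quartile of a Kaplan-Meier curve exists only if the curve gets that far. With planned clearance of 18% to 20% on vehicle and 35% to 38% on SB206, most of the quartile table would print as not estimable. What remains for this endpoint is a p-value, counts and a plot. A reader could learn that the curves differ, but not by how much or how precisely, although the protocol promises 95% confidence intervals where relevant.

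Among the exploratory endpoints that get a treatment test in section 11.3, this is the only one with no stated covariates. Baseline lesion count runs from 3 to 70 and may well influence how soon the last lesion goes. In a hazard-type analysis, leaving out a prognostic covariate pulls the treatment contrast toward the null. The SAP's reason for the simpler method is that household correlation is small and the endpoint is exploratory. That speaks to clustering. It does not explain the absence of covariates or of an estimate.

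**Working it through.** **Inputs.** From SAP section 5: 227 active and 113 vehicle subjects, two-sided alpha 0.05, and the three rate pairs. Phase 2 gave "18% (12/66) for vehicle and 38% (18/48) for SB206 12% QD and the covariate-adjusted treatment difference was 18" percent. The documents give no dropout rate, no recurrence rate and no prognostic strength for age or lesion count.

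**1. The plan's own power figures.** Two-proportion z-test, pooled variance under the null, no continuity correction. For 18% vs 36%:
- pooled rate = (113 × 0.18 + 227 × 0.36)/340 = 0.300
- null SE = √[0.300 × 0.700 × (1/113 + 1/227)] = 0.0528
- alternative SE = √[0.18 × 0.82/113 + 0.36 × 0.64/227] = 0.0482
- power = Φ[(0.18 − 1.96 × 0.0528)/0.0482] = Φ(1.59) = 94.4%

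The other pairs give 93.4% and 82.8%. The stated 94%, 93% and 83% are reproduced, so these are the right rates to use. No power is stated for time to clearance.

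**2. Which quartiles are reached.** Take the planned Week 12 rate as the height of the curve at Week 12 (no dropout, no recurrence). An arm's quartile needs 25%, 50% or 75% cleared, that is at least 29 of 113 on vehicle for the first quartile and at least 114 of 227 on active for the median. Binomial tail probabilities:

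| Arm, true rate | First quartile reached | Median reached |
|---|---|---|
| Vehicle 18% | 2.7% | 0 |
| Vehicle 20% | 8.5% | 0 |
| Active 35% | 99.9% | 0 |
| Active 36% | >99.9% | 0.001% |
| Active 38% | >99.9% | 0.012% |

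Zeros are to the precision computed. The third quartile is not reached in either arm. Only the active first quartile is expected, so five of six are not estimable under every rate pair. Since clearance is seen only at visits, that one quartile will mostly reflect a visit date.

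**3. Sensitivity.** The planned rates count dropouts as failures, whereas Kaplan-Meier censors them. With dropout fraction d, the curve can rise to roughly p/(1 − d).
- Vehicle reaches 25% at d = 1 − 0.20/0.25 = 20%, or at 1 − 0.18/0.25 = 28%.
- The active median is reached at d = 1 − 0.38/0.50 = 24%, 1 − 0.36/0.50 = 28%, or 1 − 0.35/0.50 = 30%.

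Subjects who clear and then recur before Week 12 also raise the first-clearance curve. For vehicle this would have to add 5 to 7 points, and for the active median 12 to 15 points, if it acted alone.

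**4. What an effect estimate would look like.** Under proportional hazards, HR = ln(1 − p_active)/ln(1 − p_vehicle). For 18% vs 36% this is ln(0.64)/ln(0.82) = 2.25. Expected events are 113 × 0.18 + 227 × 0.36 = 102. The approximate SE of log HR is 1/√(102.06 × 0.668 × 0.332) = 0.21, so the 95% CI would be about exp(0.810 ± 0.412) = 1.5 to 3.4. The other pairs imply HR 2.14 (109 events) and 1.93 (102 events).

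**5. Power with and without covariates.** Simulated trials, with clearance seen at Weeks 2, 4, 8 and 12, hazards set so the marginal Week 12 rates match the plan, no dropout and no clustering. An unstratified log-rank test is compared with a Cox model holding two prognostic covariates. There were 1,500 runs for the first two pairs and 2,500 for the third, so the Monte Carlo SE of each power is below 1 point. The SD of the prognostic log-hazard is an assumption.

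| SD of prognostic log-hazard | 18% vs 36%: log-rank / adjusted | 20% vs 38% | 20% vs 35% |
|---|---|---|---|
| 0 | 95.5 / 95.4 | 94.5 / 93.9 | 83.5 / 82.6 |
| 0.4 | 93.4 / 94.2 | 93.1 / 93.7 | 83.4 / 84.9 |
| 0.7 | 95.2 / 96.7 | 93.2 / 96.2 | 83.2 / 87.8 |
| 1.0 | 94.2 / 98.2 | 92.8 / 98.0 | 84.4 / 92.8 |

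The gain is about 0 points (slightly negative) with no prognostic value, about 1 at SD 0.4, 1.5 to 4.6 at SD 0.7, and 4 to 8.5 at SD 1.0.

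**The case against.** The best reply is that the timing of clearance is already estimated elsewhere. Complete clearance at Weeks 2, 4, 8 and 12 is analysed with the covariate-adjusted GEE, giving an odds ratio with 95% CI and predicted proportions with CIs. The latest SAP adds a CI for the difference. Those visits are the only times at which clearance is counted, so a grouped-time model draws on the same data. This stands, and it is the main reason the impact is small. It is not a full substitute. The visit-wise analyses count recurrences and missing visits as failures and give four separate contrasts, whereas this endpoint concerns first clearance with censoring and has no contrast at all.

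It is also fair that the endpoint is exploratory, that no power is claimed for it, and that Kaplan-Meier with a log-rank test is a valid analysis. A quartile reported as not estimable is uninformative, but it does not mislead.

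Some stronger readings are tempting but not supported:
- A reader might infer that the quartiles are the only output. Counts and percentages cleared and censored, and a plot, are also planned; none of them is a treatment effect with a CI.
- A reader might infer that the test loses power. That holds only if age or lesion count is prognostic, and the documents do not quantify this.
- A reader might infer that the SAP deliberately drops these covariates. The strata are unnamed, so the omission is inferred from the randomization factors.
- A reader might take this endpoint as the one meant to show faster resolution. The rationale speaks of accelerating resolution, but nothing ties that statement to this endpoint.

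**Conclusion.** The point holds as a minor gap in reporting and specification. At all three planning scenarios five of the six planned quartiles are not reached, and no between-arm estimate with a CI is planned. This conclusion needs no assumption about prognosis. It would weaken only with dropout of about 20% or more, substantial recurrence before Week 12, or clearance well above plan.

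The covariate part is conditional. If the strata are the randomization factors, the test leaves out age and baseline lesion count, and the power forgone runs from about zero to roughly 4 to 9 points as assumed prognostic strength goes from none to strong. The simulation left out stratification, dropout and clustering, so these figures are indicative. Even unadjusted, power is about 93% to 95% at an 18-point difference and about 83% to 84% at 20% vs 35%. The primary and secondary conclusions, the error rate and the sample size are unaffected.

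**What to change.** In SAP 11.3:

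1. Name the log-rank strata as the randomization factors (household number by investigator type) and keep the test.
2. Add a grouped-time proportional hazards model (complementary log-log link, visit as a factor) with treatment, investigator type, household number, age and baseline lesion count, and household-robust standard errors. Report the hazard ratio for clearance with its 95% CI. State whether the sparse-strata rule in section 10.3 of the latest SAP also applies here.
3. Report Kaplan-Meier cumulative first-clearance proportions with 95% CIs by arm at Weeks 4, 8 and 12, in place of the quartiles or beside them.

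The cost is one extra model and a few table rows, with no new data. The hazard ratio assumes roughly proportional hazards. It is also conditional on the covariates, so it need not match the unadjusted contrast between the plotted curves. If the covariates turn out not to be prognostic, the adjusted test may have up to about 1 point less power than the log-rank test, which is a reason to keep both.
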